12.7.2. Evaluation of response

Subjects who complete ¹⁷⁷Lu-PSMA-617 treatment and at least 12 weeks of subsequent follow-up evaluations (as described in the schedule calendar-section 6.1.) will be considered evaluable (consistent with PCWG3 guidelines). As the timing of response is not known, should the anticipated time to response be determined to be earlier than with other therapies using alternative markers of response, we may not replace subjects who are not evaluable through week 12 on study.

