As there is a reasonably large pool of short- and long-term experience with PSMA-directed 177Lu, we will transition to a phase II cohort will be enrolled at the MTD/RP2D to gain additional safety data as well as preliminary efficacy data. We will enroll up to 27 subjects in the Phase II trial utilizing a Simon two-stage design (including the 3-6 patients used for establishing the MTD). For the phase II portion, we will define evaluable patients as those who met eligibility requirements, have initiated therapy, and were not removed from the study for non-compliance or withdrawal. Sample size recommendations for the two-stage design are determined according to Simons two-stage minimax design. The first stage will accrue a total of 16 patients (including those who were treated at the MTD in the phase I portion), if 6 or fewer of the first 16 evaluable patients do not experience a 30% decline in PSA, the study will be terminated and declared to have a negative result. If 7 or more patients out of the first 16 evaluable patients experience a 30% decline in PSA, 9 more patients will be accrued in Stage 2 (total sample size of 27). The new regimen will be declared to have activity and be worthy of further testing if 13 or more patients experience a 30% PSA decline among the 27 patients who are part of the phase II trial.

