6.2.9. Imaging Plan

A. ^{68}Ga -PSMA-HBED-CC PET/CT Scan

Patient preparation should be according to the policies and procedures of the local imaging site (CIBC). The patient does not need to be fasting for either the infusion or

the scans. The use of intravenous or oral contrast will not be permitted. Specifications for acquiring the ⁶⁸Ga-PSMA-HBED-CC PET/CT scans will be provided in study specific documentation by the study chair or the co-investigators from the Division of Nuclear Medicine. PET/CT should be obtained during the Screening Visit as well as at the end of study visit. The images are acquired between 1 and 3 hours after the ⁶⁸Ga-PSMA-HBED-CC infusion. Image acquisition will be from vertex of skull to mid thighs.

B. ¹⁷⁷Lu-PSMA-617 Planar/SPECT imaging

Patient preparation should be according to the policies and procedures of the local imaging site (CIBC). The patient does not need to be fasting for either the infusion or the scans. The use of intravenous or oral contrast will not be permitted. Specifications for acquiring the ¹⁷⁷Lu-PSMA-617 planar/SPECT images will be provided in study specific documentation by the study chair or the co-investigators from the Division of Nuclear Medicine. Planar/SPECT images should be obtained during the Imaging Visit (Day 8 ±1) on all subjects after the ¹⁷⁷Lu-PSMA-617 infusion. Image acquisition will be from vertex of skull to mid thighs. Optional images will be performed on selected consenting subjects between initial Treatment Visit (between D1 - D4) and prior to Treatment Visit 2 (Day 15 ±1).

Managing toxicity

NCI CTCAE version 4.0 is used to grade all adverse events.

- Grade ≥ 2 thrombocytopenia or neutropenia within 24 hours of the second dose of ¹⁷⁷Lu-PSMA-617 (Treatment Visit 2) requires a subject's treatment to be held until the toxicity has resolved to least grade 1. If the toxicity has not resolved after 2 weeks of monitoring, the subject's ¹⁷⁷Lu-PSMA-617 treatment will be permanently discontinued and will be termed dose-limiting toxicity.

Dose-limiting toxicity (DLT) is defined as:

- Grade 4 hematologic toxicity that is deemed at least possibly related to ¹⁷⁷Lu-PSMA-617 will be termed dose-limiting toxicity.
- Any grade > 2 non-hematologic toxicity deemed to be at least possibly related to ¹⁷⁷Lu-PSMA-617 will require a subject's ¹⁷⁷Lu-PSMA-617 treatment to be permanently discontinued and will be termed dose-limiting toxicity.

Maximum Tolerated Dose (MTD) is defined as:

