6.4. Duration of Therapy and Criteria for Removal from Study

Duration of treatment portion of the study (excluding screening time) will be approximately 85 Days (± 7 days). By signing the informed consent form and agreeing to participate in this study, the subjects are required to participate in entirety up to the completion of all scheduled visits and study procedures, or until one of the following criteria applies:

- A protocol violation occurs
- Disease progression occurs
- A serious or intolerable adverse event occurs (that in the opinion of the Investigator, requires the subject's discontinuation)
- The Investigator withdraws the subject (at the Investigator's discretion for reasons other than the adverse event)
- The Principle Investigator terminates the protocol
- The subject requests to be discontinued from the protocol
- The subject is lost to follow-up
- Intercurrent illness that prevents administration of ⁶⁸Ga-PSMA-HBED-CC or ¹⁷⁷Lu- PSMA-617
- Previous anaphylactic reaction to PSMA peptides/ligands

The investigators or physicians may stop the protocol or terminate a subject's participation in the protocol at any time should they judge:

- That it is not in the subject's best interest to continue
- If the subject experiences a protocol-related injury
- If the subject needs life-saving medications/procedures/treatment
- If the subject does not comply with the study plan
- General or specific changes in the patient's condition render the patient unacceptable for further treatment in the judgment of the investigator

They may also remove the subject from the study for various other administrative and medical reasons. They can do this without the patient's consent.

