12.2. Phase II

We will enroll up to 27 subjects into the Phase II portion (including the 3-6 used for establishing the MTD). We will define evaluable patients as patients who met eligibility requirements, have initiated therapy, and were not removed from the study for non-compliance or patient withdrawal.

Sample size recommendations for the two-stage design are determined according to Simon's two-stage minimax design. We project a 30% PSA decline proportion of 35%, below which the regimen will be unacceptable and a 30% PSA decline proportion of 60%, above which the regimen will be considered worthy of further exploration. The null hypothesis that the 30% PSA decline proportion is less than or equal to 35% will be tested against the alternative hypothesis that the 30% PSA decline proportion is greater than or equal to 60%.

The sample size computations were performed assuming a 0.10 one-sided level of significance and 90% power assuming a historical control value for PSA decline of 35% and the alternative hypothesis of 60%. If 6 or fewer of the first 16 evaluable patients do not experience a 30% decline in PSA (stage 1), the study will be terminated and declared to have a negative result. If 7 or more patients out of the first 16 evaluable patients experience a 30% decline in PSA, ongoing accrual will proceed to the target sample size of 27 patients (stage 2). The new regimen will be declared active in this patient population and worthy of further testing if 13 or more patients experience a 30% PSA decline among the 27 patients entered. This two-stage design yields a 0.90 probability of a positive result if the true 30% PSA decline proportion is 60%. It yields a 0.90 probability of a negative result if the true 30% PSA decline proportion is 35%. An exact 95% binomial confidence interval will be constructed for the proportion of patients with PSA decline.

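### The plan gives two definitions of evaluable, and a third base for the final rule, for its phase II PSA test; the completer definition in Section 12.7.2 is expected to bias the response rate upward.

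*Combined protocol and SAP*

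**What the plan says.** Section 4.2 ties its definition to the efficacy part of the trial: "For the phase II portion, we will define evaluable patients as those who met eligibility requirements, have initiated therapy", with a further condition that Section 12.2 repeats, that they "were not removed from the study for non-compliance or patient withdrawal". Patients who progress, die or stop for toxicity stay in this set.

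Section 12.7.2, on evaluation of response, sets a different test. The patient must complete 177Lu-PSMA-617 treatment "and at least 12 weeks of subsequent follow-up evaluations (as described in the schedule calendar-section 6.1.) will be considered evaluable". On replacement it says only that, if response proves to occur earlier than with other therapies, "we may not replace subjects who are not evaluable through week 12 on study".

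The decision rule in Section 12.2 changes base between stages. Stage 1 reads "If 7 or more patients out of the first 16 evaluable patients experience a 30% decline in PSA". The final criterion reads "13 or more patients experience a 30% PSA decline among the 27 patients entered". Section 4.2 describes the final base as the 27 who are part of phase II.

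Three other provisions decide who falls out of the completer set:
- The toxicity rules that follow Section 6.2.9 require, for some events, "treatment to be permanently discontinued and will be termed dose-limiting toxicity".
- Section 6.4 lists "Disease progression occurs" among the reasons for leaving the study.
- Section 10.2 requires a PSA decline of at least 30%, confirmed at least 2 weeks later, with no clinical or radiographic progression in that period.

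**The concern.** The cut-offs 7/16 and 13/27 hold their error rates only if membership of the denominator does not depend on outcome. Section 12.7.2 makes it depend on outcome. A patient who leaves at early progression cannot complete the follow-up. If progression comes before a decline is confirmed, Section 10.2 also makes that patient a non-responder. Dropping such patients takes failures out of the denominator. Patients stopped for toxicity after one dose may already have had a PSA decline, so their effect is unknown.

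The two definitions do not refer to each other, nothing limits 12.7.2 to imaging response, and replacement is left open. The analysis set for the phase II primary endpoint could therefore be chosen after the data are seen. At stake are the reported proportion, its exact 95% confidence interval and, under some readings, the false-positive rate.

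**Working it through.** **Inputs.** From Section 12.2: null rate 0.35, alternative 0.60, one-sided alpha 0.10, power 0.90, stop at 6 or fewer responses in 16, positive at 13 or more in 27. The share of treated patients who fail 12.7.2 (*e*) and the share of those who are non-responders (*q*) are not in the documents. I take *e* = 5%, 10%, 20% and *q* = 100%, 75%, 65%, 50% as assumptions.

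**Step 1: reproduce the design.** With X1 ~ Bin(16, p) and X2 ~ Bin(11, p),

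R(p) = Σ over x = 7 to 16 of P(X1 = x) · P(X2 ≥ 13 − x).

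R(0.35) = 0.0979 and R(0.60) = 0.9001, so the stated error rates are right for a fixed denominator.

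**Step 2: completer set, with replacement up to 16 and 27.** If the true rate in all treated patients is 0.35, the rate among completers is

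p′ = (0.35 − e(1 − q)) / (1 − e).

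For example, with e = 10% and q = 100%, p′ = 0.35/0.90 = 0.3889. Each cell shows p′ and then R(p′).

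| q | e = 5% | e = 10% | e = 20% |
|---|---|---|---|
| 100% | 36.8%, 0.137 | 38.9%, 0.191 | 43.8%, 0.358 |
| 75% | 35.5%, 0.108 | 36.1%, 0.121 | 37.5%, 0.154 |
| 65% | 35.0%, 0.098 | 35.0%, 0.098 | 35.0%, 0.098 |
| 50% | 34.2%, 0.084 | 33.3%, 0.070 | 31.3%, 0.043 |

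The break-even is q = 65%, where the excluded respond at the same 35% as everyone else.

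**Step 3: the literal rule.** Here stage 1 needs 7 or more among the first 16 completers, and the end needs 13 or more among 27 entered. Let k be the number excluded before the 16th completer (negative binomial). The remaining 11 − k entered patients respond at 0.35. With q = 100%, the type I error is 0.102, 0.106 and 0.109 for e = 5%, 10% and 20%. It cannot exceed P(X ≥ 13) for X ~ Bin(27, 0.35), which is 0.1106, because stage 1 can only remove positive results.

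**Step 4: the estimate without replacement.** Suppose 27 are entered, 12 respond and three non-responders are dropped. The proportion moves from 12/27 = 44.4% to 12/24 = 50.0%, although the response count is unchanged.

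**Step 5: length of follow-up.** Twelve weeks after the second dose is Day 15 + 84 = Day 99. Week 12 on study is Day 1 + 84 = Day 85, the scan visit. Section 12.7.2 uses both.

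**The case against.** The strongest reply is that Section 12.2 already settles the matter. Its definition is tied to phase II, stands directly before the two-stage rule and uses the same term. Section 12.7.2 covers the whole study and names no test. On this view the references to patients entered are loose wording for the same cohort. That is the more natural reading, but the text never says so, and 12.7.2 is the section that deals with evaluability for response. The 12.2 set is not all treated patients either, since it drops withdrawals and non-compliance.

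Second, type I error inflation needs three things together: 12.7.2 governs, excluded patients are replaced, and more than 65% of them are non-responders. The documents establish none of these. This stands, and the inflated values above are conditional.

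Third, the routes out are narrow. The schedule has no radiographic evaluation between screening and Day 85, and only stops before the second dose prevent completion of both doses. PSA is drawn on Days 15, 29 and 57, so an early progressor may already show a decline, and the decision rule does not cite Section 10.2. This makes q = 100% an upper case. It does not remove the expectation that patients lost to early progression or death respond less often than those who complete follow-up.

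**Conclusion.** The concern holds. The plan gives conflicting denominators for its phase II primary test, and that part needs no assumption. The upward bias is conditional on 12.7.2 being used, and its direction is an expectation drawn from Sections 6.4 and 10.2. Its size cannot be fixed from the documents.

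Under the assumed 5% to 20% exclusion with full replacement, type I error runs from 0.137 to 0.358 if all excluded are non-responders. It runs from 0.108 to 0.154 if 75% are, and falls below the design value of 0.098 if only half are. Under the literal rule the error stays at or below 0.111, so the main effect there is on the reported proportion and its interval. This should be corrected before the phase II result is reported.

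**What to change.** Define one set for the stage 1 decision, the final test and the reported proportion with its interval: all eligible patients who received at least one 177Lu-PSMA-617 dose at the phase II dose level, including phase I patients treated at that level, with no replacement. Any patient without a qualifying PSA decline, for whatever reason, counts as a non-responder. Change both the 16 evaluable and the 27 entered to this set. Keep the 12.7.2 completers as a sensitivity analysis only, with follow-up tied to the Day 85 visit.

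The cost is wording in Sections 4.2, 12.2 and 12.7.2, and a somewhat lower observed proportion. With 16 and 27 such patients, and the 35% and 60% defined on all treated patients, alpha stays at 0.098 and power at 0.900.

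The plan must state that denominator. Section 12.2 gives 35% as a historical control without one. Published rates may rest on a subset: the German series in Section 2.3.1 reports PSA decline in 99 assessable of 145 patients, though it is not named as the source of the 35%. If both rates were meant among completers, and 5%, 10% or 20% of treated patients drop out as non-responders, the rates become 0.35(1 − e) and 0.60(1 − e). Then R gives alpha 0.068, 0.046 or 0.018 and power 0.84, 0.75 or 0.53. In that case the cut-offs or the target rates would have to be restated.

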6. STUDY PROCEDURES

Screening assessments and study procedures outlined in this section can only be performed after obtaining informed consent.

All on-study visits and dosing should be scheduled from Day 1 (date of the first infusion) on the study. It is very important that protocol procedures are performed at the time-points stipulated below. When it is not possible to perform the study visit at the exact time-point, the visit maybe performed within the acceptable visit window as defined in the visit-specific section below.

After obtaining informed consent from the enrolled subject(s), screening and study related treatment procedures will be performed as outlined in Table 8 and described in detail in Section 6.1.

7. Schedule of Evaluations Table 8: Schedule of trial events:

	Screening	Treatment Visit 1 (Day 1)	Imaging visit (Day 8±1)	Treatment Visit 2 (Day 15 ±1)	F/U Visit 1 (Day 22±3)	F/U Visit 2 (Day 29 ±3)	F/U Visit 3 (Day 43 ±3)	F/U Visit 4 (Day 57 ±3)	F/U Visit 5 (Day 71 ±3)	Scan Visit (Day 85±7)	Short-Term F/U ^k	Progression	Long-Term F/U
Informed Consent	x												
Demographics	x												
Medical History	x	x	x	x	x	x		x		x	x	x	
Physical Exam	x	x	x	x	x	x		x		x	x	x	
Performance Status	x	x	x	x	x	x		x		x	x	x	
Vital Signs ^a	x	x	x	x	x	x		x		x	x	x	
PRO ^l	x	x	x	x	x	x		x		x	x ^l	x	
CBC with diff, plts ^b	x	x	x	x ^c	x	x	x	x	x	x	x	x	
Serum Chemistry ^d	x	x	x	x	x	x	x	x	x	x	x	x	
PSA	x	x		x		x		x		x	x	x	
LDH		x		x		x		x		x	x	x	
Testosterone	x									x		x	
CTC Count ^e	x	x ^e								x			
CTC for Research ^f	x	x ^f								x			
Cell-Free DNA Research sample ^g	x	x ^g								x		x	

Immune research sample ^m	x	x ^m								x				
⁶⁸ Ga-PSMA infusion & PET CT ⁿ	x									x				
Radiographic evaluation ^h	x									x	x ^h			x ^h
¹⁷⁷ Lu-PSMA-617 infusion		x		x										
¹⁷⁷ Lu-PSMA-617 Planar/SPECT imaging ⁱ			x ⁱ	x ⁱ										
Archival Tissue	x													
Adverse Event Monitoring		x	x	x	x	x		x		x	x	x		
Concurrent Medications	x	x	x	x	x	x		x		x	x	x		
Survival Assessment ^j											x	x		

- a: Vital signs will include height and weight during screening and at least weight thereafter
- b: Any subject with grade >2 neutropenia or thrombocytopenia at any time point will be followed at least weekly until resolution to grade 1

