6.1.2. Treatment Phase

The treatment and early monitoring phase comprises of 8 visits spanning over approximately 12 weeks.

Platelets, absolute neutrophil count, bilirubin, transaminases, and serum creatinine must be performed with results available and within range of eligibility criteria within 1 week prior to treatment initiation on C1D1.

Details for each visit are listed below:

6.1.2.1 ^{177}Lu -PSMA-617 infusion (Treatment Visit 1 Day 1)

The following procedures must be completed on the day of treatment with ^{177}Lu -PSMA-617:

- Targeted Physical Examination with vital signs and weight
- Medical History
- Brief Pain Inventory, FACT-P
- ECOG Performance Status
- CBC with differential and platelet count
- CMP (with direct bilirubin with known Gilbert's syndrome)
- PSA
- LDH
- Single intravenous dose of ^{177}Lu -PSMA-617 (Dose based on the Cohort in which the subject is enrolled)
- Adverse event evaluation
- Concomitant medications
- Concomitant procedures

As stated above, platelets, absolute neutrophil count, bilirubin, transaminases, and

renal function assessment must be available within 1 week prior to treatment on D1 and meet eligibility criteria.

For Treatment Visit 2 (**Day 15 ±1 day**), grade ≥ 2 thrombocytopenia or neutropenia within 24 hours of the second dose of ^{177}Lu -PSMA-617 requires a subject's treatment to be held until the toxicity has resolved to least grade 1. If the toxicity has not resolved after 2 weeks of monitoring, the subject's ^{177}Lu -PSMA-617 treatment will be permanently discontinued and will be termed dose-limiting toxicity

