6.1.5 Progression

If a subject will not initiate a new treatment, then progression is considered to be by PCWG3 radiographic progression or clinical progression. However, if a subject has PSA progression and will initiate a new systemic therapy, then progression procedures should be performed prior to starting new therapy. Any procedure already performed for another visit within 2 weeks of the progression visit does not need to be repeated.

The following procedures must be completed during the progression visit:

- Targeted Physical Examination with vital signs and weight
- Medical History
- Brief Pain Inventory, FACT-P
- ECOG Performance Status
- CBC with differential and platelet count
- CMP (with direct bilirubin with known Gilbert's syndrome)
- PSA
- LDH
- Testosterone
- Cell-Free DNA BCT® Research blood sample
- Immune research blood sample
- Adverse event evaluation
- Concomitant medications
- Concomitant procedures

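### The completer-only rule in 12.7.2 conflicts with the phase II definition of evaluable and, if applied, can raise the descriptive CTC, CTC/LDH and RECIST response proportions

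*Combined protocol and SAP*

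**What the plan says.** Section 12.7.2 (Evaluation of response, under Reporting and Exclusions) makes response evaluability depend on completing ¹⁷⁷Lu-PSMA-617 treatment; subjects with that and "at least 12 weeks of subsequent follow-up evaluations (as described in the schedule calendar-section 6.1.) will be considered evaluable". It adds that, if response proves to come earlier than with other therapies, "we may not replace subjects who are not evaluable through week 12 on study". It does not say how a non-evaluable subject is counted.

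Sections 4.2 and 12.2 give a second definition, for the phase II portion: eligible, therapy started, and not removed for non-compliance or withdrawal. It does not require 12 weeks of follow-up, so it keeps early progressors.

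Section 10.1 defines CTC response, CTC below 5 with normal LDH, undetectable CTC, and a 50% CTC decline, all read at the Day 85 (12-week) visit. The Analysis of Efficacy text in 10.8 estimates the RECIST, CTC and CTC/LDH proportions as binomial proportions with 95% confidence intervals. Neither section cites 12.7.2 or 12.2, and neither says what to do with a missing Day 85 result.

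Three other provisions determine who can be missing:

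- Section 6.4 requires participation up to "completion of all scheduled visits and study procedures, or until one of the following criteria applies", and one of the criteria is "Disease progression occurs".
- Section 6.1.5 introduces its list with "The following procedures must be completed during the progression visit". The list includes PSA and LDH but no CTC count. In Table 8 the only CTC count after treatment is at Day 85.
- Section 6.1.2 says that if cytopenia at the second dose has not resolved after two weeks, "treatment will be permanently discontinued and will be termed dose-limiting toxicity".

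**The concern.** Patients who leave before Day 85 because of progression, death or a switch of therapy are likely to include treatment failures. A rule that admits only completers takes them out of the denominator. For CTC there may be no later value with which to classify them. The rule also removes a patient who received one dose, even if he attends Day 85 and has a usable result.

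The secondary proportions would then describe a selected group. They would appear beside a phase II PSA result that rests on the wider set in 12.2. In phase I the exclusions could fall unevenly across dose levels, and 12.1 allows summaries by dosing regimen in cohorts of at most six.

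**Working it through.** **The plan's own figure.** The only formal sample-size figure is the two-stage design in 12.2: continue if at least 7 of 16 respond, declare active if at least 13 of 27 respond. Summing Bin(16, π) at x₁ = 7 to 16 times P[Bin(11, π) ≥ 13 - x₁] gives 0.0979 at π = 0.35 and 0.9001 at π = 0.60. The stated 0.10 level and 90% power are reproduced. This design uses the 12.2 definition, so what follows does not touch it.

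**Which rule applies where.**

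| Patients | 12.7.2 (completers) | 4.2/12.2 (phase II portion) |
|---|---|---|
| Phase I cohorts | the only response-evaluability rule available | does not apply, except to those at the MTD who are carried into phase II |
| Phase II (up to 27) | applies by its heading | also applies, and conflicts |

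**Who is dropped under 12.7.2.** Anyone without both doses, and anyone who stops before 12 weeks. A radiographic progressor has a scan, and 10.8 uses scans done as clinically indicated. He could therefore be classified for RECIST, but 12.7.2 still makes him non-evaluable if he stops early. The RECIST part is weaker for that reason.

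**Size.** Let n be the number treated, k the number dropped, p the response rate among those retained, and r the rate the dropped patients would have had.

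- Completer proportion: p
- All-treated proportion: [(n - k)p + kr]/n = p - (k/n)(p - r)
- Overstatement: (k/n)(p - r)

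The documents give neither k nor r. Assuming p - r = 0, 0.25 or 0.50, the overstatement in percentage points is:

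| n | k | p - r = 0 | 0.25 | 0.50 |
|---|---|---|---|---|
| 27 | 1 | 0 | 0.9 | 1.9 |
| 27 | 3 | 0 | 2.8 | 5.6 |
| 27 | 6 | 0 | 5.6 | 11.1 |
| 6 | 1 | 0 | 4.2 | 8.3 |

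Check with n = 27, k = 3 and 12 responders among the 24 retained:

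- Completers: 12/24 = 50.0% (exact 95% CI 29.1 to 70.9)
- All treated, none of the 3 would have responded: 12/27 = 44.4% (25.5 to 64.7), difference 5.6 points
- All treated, 1 of the 3 would have responded: 13/27 = 48.1% (28.7 to 68.1), difference 1.9 points

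**Timing of the 12 weeks.** Section 6 says "All on-study visits and dosing should be scheduled from Day 1 (date of the first infusion) on the study". From Day 1, (85 - 1)/7 = 12.0 weeks, and the ±7-day window runs from Day 78 to Day 92, which is 11.0 to 13.0 weeks. Counted instead from the second dose on Day 15, 12 weeks ends on Day 15 + 84 = Day 99, after that window closes. Read literally, the first sentence of 12.7.2 would exclude a patient who attends every visit through Day 85 and then stops. Its later reference to week 12 on study fits the Day 1 count.

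**The case against.** Four arguments carry weight.

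First, nothing in 10.1 or 10.8 invokes 12.7.2. Section 10.1 speaks of all subjects having samples drawn, and 10.8 of subjects enrolled and, for response categories, of those with measurable disease. That 12.7.2 sets the denominator is therefore an inference. This stands, and the point is conditional because of it. But those phrases do not say how a missing result is counted, and 12.7.2 is the section headed for response.

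Second, the definition in 4.2 and 12.2 is written for the phase II portion as a whole, not for PSA alone. This also stands. For the 27 phase II patients the defect is a conflict between two definitions. Only in phase I does 12.7.2 stand alone.

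Third, few patients may be lost. No conventional scan is scheduled between screening and Day 85. Under 6.1.5, "If a subject will not initiate a new treatment, then progression is considered to be by PCWG3 radiographic progression or clinical progression", so a PSA rise alone does not remove a patient who starts nothing new. k may be zero. For CTC below 5, r is probably above zero, because patients who stay below 5 count as responders.

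Fourth, the shift in the example is small beside confidence intervals about 40 points wide, and 12.5.2 makes these analyses descriptive. This limits the severity. It does not justify leaving the denominator open.

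A reader might also infer that dropping one-dose patients inflates the result. The documents do not support a direction: these men are stopped for toxicity, and nothing links that to CTC or RECIST response. Nor does 12.7.2 show that replacement is the default; it says only that subjects may not be replaced in one circumstance.

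**Conclusion.** The point holds in a conditional form and is minor. The plan has two definitions of evaluable, ties neither to the CTC, CTC/LDH and RECIST proportions, and has no rule for a missing Day 85 result. If 12.7.2 is followed, the proportions are too high by (k/n)(p - r) whenever the dropped patients would have responded less often than those retained. With 27 patients, each one dropped adds 3.7 points × (p - r). The total cannot be derived from the documents and may be zero.

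A reader might infer that the phase II activity conclusion is biased too. It is not: the PSA decision rule uses the 12.2 definition, which keeps early progressors, and no decision rule uses the secondary proportions. Early progressors also remain in the Kaplan-Meier analyses of progression-free and overall survival. Nor do the documents support a large effect: a shift above 10 points, as with k = 6 in the table, needs a loss of 6 of 27 and a gap of 0.50, and both are assumptions.

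**What to change.** Change the wording as follows.

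1. In 12.7.2, replace the completer rule with all treated patients, and cite it in 10.1 and the 10.8 analysis text. For RECIST, restrict to those with measurable disease at baseline; for the 50% CTC decline, to those with a detectable baseline count. The 12.2 definition stays for the PSA decision rule.
2. Count as non-responders patients with no Day 85 result because of progression, death or new systemic therapy. Classify one-dose patients by their Day 85 result.
3. Report how many results are missing for other reasons (adverse event, withdrawal, loss to follow-up, failed sample). Give two sensitivity analyses, one counting these as non-responders and one excluding them.
4. Anchor the 12 weeks to the Day 85 ±7 visit counted from Day 1.

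The cost is text in three places and slightly lower reported secondary proportions. No procedure is added. Progressed patients should not be required to undergo the Day 85 scans or PET: 6.4 now releases them, and the rule in item 2 classifies them without those scans.
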